16.1 Pharmacokinetics

16.1.1 General Considerations

Population: PK analysis set

Pharmacokinetic parameters will be calculated using actual collection time data where available. There will be no rounding of actual time values, and full precision values will be used as calculated from eCRF data. In the case that the actual time is not available, the scheduled time will be used. Predose samples that occur before drug administration will be assigned a time of 0 hours for that FD, as if the sample had been taken simultaneously with the study drug administration.

Values below the lower limit of quantitation of the assay (LLOQ) will be taken as zero for summary statistics of PK concentration data.

In case of concentrations above the upper limit of quantitation (ULOQ) the numeric value of the actual ULOQ of the bioanalytical assay may be used for preliminary, draft PK evaluations only. For final evaluations >ULOQ values are not accepted and should be replaced by valid numeric values from dilution measurement.

Missing concentrations (e.g., no sample, insufficient sample volume for analysis, no result or result not valid) will be reported and used generally as "N.R.". There will be no imputation for missing concentrations.

Pharmacokinetic concentrations which are erroneous due to a protocol violation, as defined in the clinical trial protocol (CTP), documented handling error or analytical error (as documented in the bioanalytical report) may be excluded from the PK analysis if agreed upon with sponsor PK analyst/clinical pharmacologist prior to performing the statistical analysis. Any PK concentrations excluded from the PK analysis set will be listed and flagged, and the rationale for exclusion will be listed and provided in the CSR. Any other PK concentrations that appear implausible to the Pharmacokineticist must not be excluded from the analysis. Any implausible data will be discussed in the CSR.

Individual PK concentrations in plasma for M3541 will be listed and summarized by dose and fraction day using standard descriptive statistics. A listing of PK blood sample collection times as well as derived sampling time deviations will also be provided.

Pharmacokinetic parameters for M3541 will be listed and summarized by dose and fraction day using standard descriptive statistics (see TFLs for further information). PK parameters derived with inclusion of flagged concentrations will not be used in the descriptive statistics.

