16.1.2 Estimation of Individual Pharmacokinetic Parameters

Population: PK analysis set

The final analysis will be performed IQVIA and reviewed by the Clinical PK/PD Group of quantitative pharmacology (QP), Merck, Darmstadt, Germany. Standard non-compartmental methods will be used to calculate PK parameters using the actual administered dose and the actual elapsed time since dosing, given with a precision of 14 significant digits or the SAS format Best12. In cases where the actual sampling time or dose is missing, calculations will be performed using the scheduled time or dose level. Otherwise, there will be no further imputation of missing data. The following PK parameters will be calculated for the determination of the PK profile of M3541, where appropriate for Fraction Day 1, 2 to 6, or 9:

Symbol	Definition
AUC _{0-6h}	The area under the concentration-time curve (AUC) from time zero (= dosing time) to the 6-hour sampling time. Calculated using the mixed log linear trapezoidal rule (linear up, log down). (FD 1 and 9 only)
AUC _{0-t}	The AUC from time zero (= dosing time) to the last quantifiable sampling time (t _{last}) at which the concentration is at or above the lower limit of quantification. Calculated using the mixed log linear trapezoidal rule (linear up, log down) (FD 1 and 9 only).

Symbol	Definition
AUC _{0-t} /Dose	The Dose normalized AUC from time zero to the last sampling time (t _{last}) at which the concentration is at or above the lower limit of quantification. Normalized using the actual dose, using the formula AUC _{0-t} /Dose. (FD 1 and 9 only)
AUC _{0-∞}	The AUC from time zero (dosing time) extrapolated to infinity, based on the predicted value for the concentration at t_{last} , as estimated using the linear regression from λ_z determination. AUC _{0-∞} =AUC _{0-t} +C _{last pred} / λ_z . (FD 1 only)
AUC _{0-∞} /Dose	The Dose normalized AUC from time zero extrapolated to infinity. Normalized using actual dose, using the formula $AUC_{0-\infty}/Dose$. Predicted $AUC_{0-\infty}$ should be used. (FD 1 only)
AUC _{0-τ}	The AUC from time zero (dosing time) extrapolated to the end of the dosing interval (24 h). (FD 9 only)
CL/f	The apparent total body clearance of drug following extravascular administration, taking into account the fraction of dose absorbed. $CL/f = Dose/AUC_{0-\infty}$. Predicted $AUC_{0-\infty}$ should be used. (FD 1 only)

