CL _{SS/f}	The apparent total body clearance of drug at steady state following extravascular administration, taking into account the fraction of dose absorbed. $CL_{ss//f} = Dose / AUC_{0-\tau}$ where $AUC_{0-\tau} = AUC$ extrapolated to 24h (FD 9 only)
C_{max}	Maximum observed concentration for each fraction day. (FD 1 and 9 only)
C _{max} /Dose	The dose normalized maximum concentration. Normalized using the actual dose, and the formula $C_{\text{max}}/Dose$. (FD 1 and 9 only).
C _{trough}	The concentration observed immediately before next dosing (corresponding to predose or trough concentration for multiple dosing). (FD 2 to 6 and FD 9)
C _{2.25h}	The concentration observed at 2.25 h post dose. (FD 1-6 and 9)
C _{min}	Minimum observed plasma concentration collected during a dosing interval. (FD 9 only)
Cavg	Average plasma concentration during a dosing interval. $C_{avg} = AUC_{0-\tau}/\tau$. (FD 1 and 9 only)

Symbol	Definition
R _{acc(AUC0-6h)}	The accumulation ratio to assess the increase in exposure via AUC_{0-6h} . $R_{acc(AUC0-6h)}=(AUC_{0-6h} \text{ after multiple dose}) / (AUC_{0-6h} \text{ after single dose}). (FD 9 only)$
R _{acc(Cmax)}	The accumulation ratio to assess the increase in maximum concentration with multiple dosing. $R_{acc(Cmax)} = (C_{max} \text{ after multiple dose})/(C_{max} \text{ after single dose})$ (FD 9 only)
t _{1/2}	Apparent terminal half-life. $t_{1/2} = \ln (2)/\lambda_z$. (FD 1 only)
t _{max}	The time to reach the maximum observed concentration collected during a dosing interval (unless otherwise defined, take the first occurrence in case of multiple/identical C _{max} values). (FD 1 and 9 only)
t _{min}	The time to reach the minimum observed concentration collected during a dosing interval. (FD 9 only)
Vz/f	The predicted apparent volume of distribution during the terminal phase following extravascular administration, based on the fraction of dose absorbed. $V_z/f = Dose/(AUC_{0-\infty}*\lambda_z)$ following single dose. (FD 1 only)
λ_z	Terminal first order (elimination) rate constant. Determined from the terminal slope of the log-transformed concentration curve using linear regression on terminal data points of the curve. (FD 1 only)

FD 9 parameters should only be included in descriptive statistics if 4 consecutive days of treatment with no interruption were given to the patient. PK parameters not included in descriptive statistics will be flagged. Any flags should be included in the study specific SDTM/ADaM.

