The following PK parameters will be calculated for diagnostic purposes (Fraction Day 1 only) and listed, but will not be summarized:

- The time interval (h) of the log-linear regression ($\lambda_{z \text{ low}}$, $\lambda_{z \text{ upp}}$) to determine λ_z .
- Number of data points (N_{λ}) included in the log-linear regression analysis to determine λ_z .
- Goodness of fit statistic (Rsq,adj) for calculation of λ_z .

The AUC from time t_{last} extrapolated to infinity given as percentage of $AUC_{0-\infty}$ AUCextra% = (extrapolated area/AUC_{0-∞})*100 The regression analysis should contain data from at least 3 different time points in the terminal phase consistent with the assessment of a straight line on the log-transformed scale. Phoenix WinNonlin best fit methodology will be used as standard. The last quantifiable concentration should always be included in the regression analysis, while the

concentration at t_{max} and any concentrations <LLOQ which occur after the last quantifiable data point should not be used.

AUCextra% should be < 20%, the coefficient of correlation (Rsq, adj) should be \ge 0.8 and the observation period over which the regression line is estimated should be at least two-fold the resulting $t_{1/2}$ itself. If these criteria are not met, then the rate constants and all derived parameters (e.g., CL, and Vz, etc.) will be included in the parameter outputs and descriptive statistics but will be flagged and discussed appropriately. Any flags should be included in the study specific SDTM/ADaM.

Partial areas AUC_{0-6h} should be calculated using the scheduled dosing interval, as defined in the CTP. The actual dosing interval calculated from eCRF time data should not be used. The following rules apply when calculating the partial area AUC_{0-6h} within the observed time interval from T_1 to T_2 :

- If the start time of the interval (T₁) occurs before the first observation, the observation at T₁ will be estimated using the linear interpolant between the first data point and initial concentration at time zero (C0). For single dose data C0= 0 when the drug was administered via an extravascular route or via infusion, and C0 is the estimated dosing time intercept when the drug was administered as an IV bolus. For steady state models, C0 is the minimum concentration value occurring within the time interval T₁ to T₂.
- If either T₁ or T₂ falls within the time range in which samples were taken, but does not

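### The SAP summarises and plots FD 1 half-life, AUC0-∞, CL/f and Vz/f from fits that its own acceptance rules would fail, and drops the protocol's end-of-treatment half-life without recording it

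*SAP*

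**What the plan says.** **Parameters and days.** SAP 16.1.2 determines λz "using linear regression on terminal data points of the curve. (FD 1 only"). It gives the same FD 1 restriction to t1/2, AUC0-∞, AUC0-∞/Dose, CL/f and Vz/f. The parameter table applies "where appropriate for Fraction Day 1, 2 to 6, or 9".

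**Acceptance rules.** "The regression analysis should contain data from at least 3 different time points in the terminal phase". The extrapolated share should be below 20%, adjusted Rsq at least 0.8, and "the observation period over which the regression line is estimated should be at least two-fold the resulting" half-life. Values that miss these criteria "will be included in the parameter outputs and descriptive statistics but will be flagged and discussed appropriately". SAP 16.1.1 also uses FD 1 AUC0-∞ in the dose-proportionality scatter plot.

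**Sampling.** For the once-per-FD schedule, protocol Table 4 has FD 1 PK samples to 6 h, and footnote c makes the 8 h and 12 h samples optional. The full end-of-treatment profile is on FD 10, with later samples at 72 h (optional) and 240 h. There is no FD 9 PK sample in that table.

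**What the protocol knows and asks for.** Protocol 3.1.4 predicted a half-life of about 8 h. Protocol 3.1.5 reports a preliminary value above 48 h and says that sampling built for daily dosing gave an accurate Cmax but not PK parameters for a half-life beyond 24 h. Protocol 8.3.2 lists t1/2, AUC0-∞, CL/F and Vz/F for FD 1, and lists t1/2 again for FD 9 or 10. SAP section 7 records two changes from the protocol (the pain summaries and the unexplored intermittent schedules) and nothing about half-life.

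**The concern.** A log-linear fit over the first 6 to 12 hours cannot describe the terminal phase of a drug whose half-life is measured in days. The SAP's acceptance rules should stop such a fit from being read as terminal. Here they only attach a flag, and the value still enters the means and geometric means. If almost every accurate fit fails, the summary table consists largely of failures.

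The later samples that could inform the half-life are collected but not used for it, because the end-of-treatment t1/2 is absent from the SAP. The remaining end-of-treatment parameters are tied to FD 9, a day on which subjects under protocol v5.0 give no PK sample.

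At stake is a secondary objective: the reported half-life, clearance and volume, and the reading of dose proportionality from AUC0-∞.

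**Working it through.** The plan gives no figure to reproduce, and the half-life above 48 h cannot be re-derived because no concentrations are given. The check is whether an accurate FD 1 fit can meet the SAP's own rules.

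**Inputs.** Last sample at 6 h (mandatory), or 8 h or 12 h (optional), from protocol Table 4. Half-life 48 h (protocol 3.1.5), 8 h (protocol 3.1.4), and 24 h for range. tmax about 2 h, since protocol 8.4 puts twice tmax at about 4 h. The SAP excludes the tmax point, so the first usable sample is at 2.25 h.

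**Extrapolated share.** For a mono-exponential curve the share is 2^(−t_last/t½). At 48 h and 6 h this is 2^(−0.125) = 91.7%.

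| t½ | to 6 h | to 8 h | to 12 h | to 24 h | limit |
|---|---|---|---|---|---|
| 48 h | 91.7% | 89.1% | 84.1% | 70.7% | <20% |
| 24 h | 84.1% | 79.4% | 70.7% | 50.0% | <20% |
| 8 h | 59.5% | 50.0% | 35.4% | 12.5% | <20% |

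The 24 h column would need the FD 2 predose sample in the FD 1 profile. SAP 16.1.1 does not place it there: "Predose samples that occur before drug administration will be assigned a time of 0 hours for that FD". At 48 h it would fail in any case.

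**Span.** Available: 6 − 2.25 = 3.75 h, 8 − 2.25 = 5.75 h, 12 − 2.25 = 9.75 h. Needed: 2 × 48 = 96 h, or 2 × 8 = 16 h at the predicted value. Conversely, the longest half-life that can pass with sampling to 12 h is 9.75/2 = 4.9 h. The rule therefore flags accurate fits and can pass only short, early-phase ones.

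**Illustration of the size of error (assumed model).** C = f·exp(−at) + (1−f)·exp(−bt) − exp(−ka·t), with terminal half-life 48 h, f = 0.5, 0.7, 0.8 or 0.9, early half-life 2, 3 or 4 h, and ka = 1.5/h: 12 settings, best adjusted-Rsq fit.

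| FD 1 sampling to | fitted t½ | settings passing all rules |
|---|---|---|
| 6 h | 3.1–11.2 h | 0 of 12 |
| 8 h | 3.3–11.8 h | 0 of 12 |
| 12 h | 4.2–21.8 h | 2 of 12 (4.2 h and 4.6 h) |

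**Post-FD 10 profile, same model.** Ten doses are summed, and one mono-exponential setting is added (13 in all).

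| true t½ | with 72 h sample | 240 h sample only |
|---|---|---|
| 48 h | 36.9–48.0 h | 38.3–48.0 h |
| 72 h | 52.4–72.0 h | 54.9–72.0 h |

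All 13 pass the point-count, Rsq and span rules. The worst understatement is 1 − 36.9/48 = 23% and 1 − 52.4/72 = 27% with the 72 h sample, and 20% and 24% without it. Without it, adjusted Rsq is at least 0.99 in every setting, so Rsq does not reveal the curvature.

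**Subjects before v5.0.** In SAP Table 4 (ECG times, which protocol 7.4.4 links to PK), FD 9 is at 240 h and the late samples are at 312 h and 480 h. The FD 10 dose falls at 264 h, so only two scheduled samples follow it, at 48 h and 216 h after that dose. The weekend break also gives two: 2.25 h after the FD 5 dose, and FD 6 predose at 168 − 96 = 72 h. Three are required.

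**Choice of plot variable.** AUC0-t is "The AUC from time zero (= dosing time) to the last quantifiable sampling time", so its end moves with the optional samples. At t½ 48 h and ka 1.5/h (assumed), AUC to 12 h is 2.04 times AUC to 6 h for the same curve.

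**The case against.** **The SAP follows the protocol.** This stands for AUC0-∞, CL/f and Vz/f, and for the FD 1 half-life: protocol 8.3.2 lists all of them at FD 1. A reader might infer that the SAP departed from the protocol on these. It did not. The departures are the missing FD 9 or 10 half-life and the PK days not carried forward to FD 10.

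**The failures are disclosed.** Also true. Values are flagged and discussed, and the regression interval, point count, fit statistic and extrapolated share are covered: "The following PK parameters will be calculated for diagnostic purposes (Fraction Day 1 only) and listed, but will not be summarized". A reader might infer that poor fits are concealed; the documents show otherwise. But a flag in a listing does not remove a value from a geometric mean. The SAP 16.1.1 rule that keeps some parameters out of the summaries concerns flagged concentrations, not failed λz criteria.

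**The post-FD 10 fit has its own bias.** This stands. Every such fit leans on samples at or before 6 h plus one or two late points, and the 240 h point dominates Rsq. The model behind the bias figures is assumed, so neither the bias nor the gain is established by the documents.

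**Earlier subjects may not be a lost cause.** It is tempting to say that no half-life can be estimated for them. That goes too far: protocol 3.1.5 obtained its preliminary value from concentrations on a non-treatment day and before dosing after the weekend, and the SAP's general rule includes unscheduled assessments. The scheduled samples fall short of three, but individual subjects may not.

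**Conclusion.** The concern holds for the λz-dependent FD 1 parameters. With the half-life that the protocol reports, an accurate fit misses the extrapolation limit by a factor of more than four (84–92% against 20%) and the span rule by about tenfold or more (at most 9.75 h against 96 h). The conclusion does not depend on the preliminary 48 h, because the originally predicted 8 h fails too. It rests on mono-exponential decline after a tmax of about 2 h; the two-phase figures are illustration only.

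The omission of the protocol's FD 9 or 10 half-life without a section 7 entry, and the FD 9 labels for subjects sampled on FD 10, are plain inconsistencies between the documents.

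A reader might go further and doubt the dose-finding result. The documents do not support that: the MTD is determined from DLTs in the DLT Analysis Set, and Cmax and AUC0-6h do not depend on the terminal slope. The affected outputs are secondary and descriptive. The change should be made, but the primary objective does not hang on it.

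**What to change.** 1. **FD 1.** List λz-dependent values that fail the criteria, with flags, but leave them out of the descriptive statistics and the dose-proportionality plot; use FD 1 AUC0-6h and Cmax there. Report any FD 1 value that passes as an apparent early-phase value with its regression interval, not as the terminal half-life.
2. **Subjects under v5.0.** Change every FD 9 PK profile parameter in the SAP to FD 10. Restore t1/2 from the post-FD 10 profile, summarising only fits that include the 240 h sample and meet the point-count, adjusted Rsq and span rules. Mark separately the fits without the 72 h sample, and state that t1/2 may be understated.
3. **Earlier subjects.** Report t1/2 only where at least three quantifiable samples follow a dose with no intervening dose; otherwise list it as not estimable.
4. **Record.** Enter these changes in SAP section 7.
5. **Separate point.** Reconcile protocol Table 4 footnote d with its own columns. The footnote equates 72 h and 240 h with PTD 1 and PTD 8, but under Table 1 footnote b PTD 1 is the day after FD 10, which gives 24 h and 192 h. SAP Table 4 (264 + 72 = 336 h; 264 + 240 = 504 h) and protocol Figure 1 (PTD 3 and PTD 10) agree with the hours.

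**Cost.** SAP wording, a section 7 entry and one protocol footnote. Few or no FD 1 AUC0-∞, CL/f and Vz/f values would be summarised, although they are protocol endpoints. Half-life may be missing for many of the at least 8 subjects dosed before v5.0. For v5.0 subjects it depends on a quantifiable 240 h sample: its visit is not in protocol Table 1, the assay limit is not given, and in the illustration the level by then is 1–10% of Cmax.

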#### Table 4 Electrocardiogram, Pharmacokinetic, and Biomarker Assessments: M3541 Once per FD Dosing Schedule

ECG = electrocardiogram; FD = Fraction Day (days when RT and M3541 are given); PK = pharmacokinetics; PTD = post-treatment day.

a. 12-lead resting ECGs will be obtained after the subject has been in semi-supine position for at least 5 minutes and evaluated by the Investigator for safety assessment. All ECGs should be collected prior to any blood draws for routine clinical laboratory samples or any associated PK blood sample draws. The ECG should be obtained using a Holter recorder. An ECG on PTD 1 is only required if the PTD 1 optional PK sample is drawn.

b. At the indicated times, additional digital ECG recordings equivalent to triplicate ECGs are to be recorded for quantitative analysis by a central ECG laboratory (after the end of the study). The ECG recordings must be acquired immediately prior to the PK sample scheduled for the same time point. The ECG should be obtained using a Holter recorder.

- c. The 8 and 12 hour PK samples and ECG assessments are optional.
- d. The 72 and 240-hour timepoints correspond to PTD 1 and 8, respectively. The 72-hour PK sample is optional and will only be taken if the patient has a visit on PTD 1.
- e. The predose sample should be taken within 1 hour before dosing at each sampling day. PK and pharmacodynamic sampling should occur after any required ECG recording.

Table 5Electrocardiogram, Pharmacokinetic, and Biomarker Assessments: Thrice Weekly Intermittent M3541Dosing Schedule: Monday / Wednesday / Friday

	Predose	Hours Postdose (± minutes)										
		1 (± 5)	3 (± 30)	4 (± 30)	6 (± 30)	8 (± 30)	12 (± 30)	24 (± 120)	26 (± 120)	72 (± 24h)	240 (± 24h)	
Electrocardiogram a												
FD 1 (M3541 dosing)	Xp	Xp	Xp	Xp	Xp	X b,c	X b,c	X b,d	X b,d			
FD 3, 5, 6, and 8 (M3541 dosing)	Х		Х									
FD 10 (M3541 dosing)	Xp	Xp	Xp	Xp	Xp	X b,c	X b,c			X b,e	X b,e	
Pharmacokinetic f												
FD 1 (M3541 dosing)	Х	Х	Х	Х	Х	Xc	Xc	Xd	Xď			
FD 3, 5, 6, and 8 (M3541 dosing)	Х		Х									
FD 10 (M3541 dosing)	Х	Х	Х	Х	Х	Xc	Xc			Xe	Xe	
Plasma protein determination												
FD 1	Х											
FD 10	Х											
Pharmacodynamic marker CC												
FDs 1, 6, and 8	Х	Х	Х					FD 1 only				
FD 2	Х											
Immune cell sampling f												
FDs 1, 6, and 9	Х											

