 coincide with an observed data point, then a linear or logarithmic interpolation is
 performed to estimate the corresponding concentration value. Whether a linear or
 logarithmic interpolation is used will depend on the method of AUC calculation, e.g.,
 linear up log down.
- If the end time of the interval (T₂) occurs after the last measurable concentration and the terminal regression (λ_z) is estimable, then λ_z is used to estimate the concentration at time T₂. The log trapezoidal rule will be used to calculate the area from the last observation time to the end time of the partial area (T₂). If λ_z cannot be estimated the partial area will not be calculated.

Potential drug accumulation will be evaluated by individual accumulation ratios for AUC_{0-6h} , C_{max} , $R_{acc(AUC_{0-6h})}$ and $R_{acc(C_{max})}$ (that will be calculated by dividing the values obtained after multiple dose (e.g., on Fraction Day 9) by the values obtained after single dose (e.g., Fraction Day 1) and summarized descriptively for each dose level.

Concentrations below LLOQ, which are before the last quantifiable data point, will be taken as zero for calculating the AUC. Unless otherwise specified in the CTP, predose samples that occur before the first drug administration will be assigned a time of 0 hours, as if the sample had been taken simultaneously with the study drug administration. The same applies to the very first predose sample of a multiple-dose study.

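### FD 1 AUC0-6h, and with it the AUC accumulation ratio, can be lost after a protocol-compliant early 6 h sample, although the FD 2 predose sample could close the interval

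*SAP*

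**What the plan says.** **Interval and times.** SAP 16.1.2 computes AUC0-6h over the scheduled interval: "The actual dosing interval calculated from eCRF time data should not be used". SAP 16.1.1 uses actual sampling times for PK parameters: "There will be no rounding of actual time values, and full precision values will be used as calculated from eCRF data".

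**Partial-area rules (SAP 16.1.2).** If an end of the interval lies inside the sampled range but does not "coincide with an observed data point, then a linear or logarithmic interpolation is" performed, without lambda-z. If the end lies after the last measurable concentration, lambda-z supplies the missing concentration. If lambda-z "cannot be estimated the partial area will not be calculated".

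**Lambda-z (SAP 16.1.2).** It needs at least three terminal points, excluding the one at tmax, and is derived for FD 1 only. Failing the criteria on extrapolated area, adjusted Rsq or length of the observation period leads to a flag, not to a missing value.

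**Sampling (protocol Table 4).** FD 1 samples are predose and 0.5, 1, 1.5, 2.25, 3, 4 and 6 h, the last with a ±30 minute window. Beyond that, "The 8 and 12 hour PK samples and ECG assessments are optional". A predose PK sample is scheduled on FD 2, within 1 hour before dosing.

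**Predose convention (SAP 16.1.1).** "Predose samples that occur before drug administration will be assigned a time of 0 hours for that FD". Nothing says that such a sample may also close the previous day's profile.

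**Use.** Protocol 8.3.2 lists FD 1 AUC0-6h and the AUC accumulation ratio among the secondary PK endpoints. SAP 16.1.2 defines that ratio as multiple-dose over single-dose AUC0-6h.

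**The concern.** A site can follow the protocol exactly, draw the 6 h sample at 5 h 45, and leave the analysis 15 minutes short of the interval end. The SAP then makes an early-window area depend on a terminal slope. Protocol 3.1.5 itself says that daily-dosing sampling gave an accurate Cmax but not the parameters of a drug whose half-life exceeds 24 h. If the slope cannot be estimated, the area is dropped and the subject has no AUC accumulation ratio.

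Cohorts are about three subjects, so one lost value matters to a dose-level summary. Protocol 3.1.5 also reports unexpected accumulation as part of the reason for modifying the schedule. The loss is avoidable, because a sample that reflects only the first dose is already scheduled for the next morning.

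**Working it through.** The plan states no figure for this point, so there is none to reproduce. The check applies the SAP's rules to possible sampling times and then asks how often lambda-z would fail.

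**1. Which FD 1 profiles lose AUC0-6h**

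| 6 h sample drawn at | Later FD 1 sample | Lambda-z | AUC0-6h |
|---|---|---|---|
| 6.00 to 6.5 h | any | not needed | calculated |
| 5.5 to 5.99 h | 8 h or 12 h, quantifiable | not needed | interpolated |
| 5.5 to 5.99 h | none | estimable, even if flagged | extrapolated to 6 h |
| 5.5 to 5.99 h | none | not estimable | missing |

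Only the last row loses the value.

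**2. When lambda-z fails**

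- Too few points: with 3, 4 and 6 h as the last samples, an observed tmax at 3 h or later leaves at most two points after tmax.
- No negative slope: at a 48 h half-life (protocol 3.1.5 gives more than 48 h), the terminal fall from 3 to 6 h is 1 − 2^(−3/48) = 4.2%. Ordinary residual error can hide that.

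**3. How often**

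The inputs below are assumptions. The documents give no absorption rate, distribution phase, residual error or actual draw times.

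*Lambda-z not estimable* (6 h sample at 5.75 h, nothing later; absorption rate 1 or 2 per h; no distribution phase, or one making up 40% of the profile with a 2 h half-life; residual CV 5 to 15%):

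- half-life 48 h: 5% to 98%
- half-life 72 h: 6% to 98%
- half-life 8 h (the pre-study prediction): 0% to 67%

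*AUC0-6h missing* (half-life 48 h, residual CV 5 to 20%, draws spread evenly over the windows so that half of the 6 h samples are early, no 8 h sample):

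- one compartment, absorption rate 1.5 per h: 40 to 41%
- the same with a 3 h distribution phase: 16 to 28%
- profiles with true tmax about 2.0 to 2.1 h: 14 to 34%
- profiles with true tmax about 1.4 h: 3 to 31%

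The 40% case has a true tmax of ln(1.5/0.0144)/(1.5 − 0.0144) ≈ 3.1 h, with 0.0144 = ln 2/48. The documents point to about 2 h: the PK analysis set definitions (protocol 8.4, SAP 8.2) equate twice tmax with about 4 h.

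If no subject in a cohort of three has a later FD 1 sample, the chance of losing at least one value is 1 − (1 − p)³: 1 − 0.97³ = 9% at p = 3%, and 1 − 0.60³ = 78% at p = 40%.

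**4. What the FD 2 predose sample does**

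Placed at about 23.5 h after the first dose, it puts 6 h inside the sampled range, so the SAP's interpolation rule applies. With the 6 h sample at 5.75 h, the piece to be closed is about 3 to 5% of AUC0-6h. In the simulated profiles, closing it this way differed from using the true decline by at most 0.04% of AUC0-6h.

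**5. The numerator**

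SAP 16.1.2 takes the numerator from FD 9 but derives lambda-z on FD 1 only. An early 6 h sample on FD 9 has no lambda-z to fall back on, and the SAP lists no FD 10 trough to bracket it. Protocol Table 4 now puts the end-of-treatment profile on FD 10, with samples at 72 h (optional) and 240 h and no further dose. Those could bracket 6 h if quantifiable and treated as part of that profile.

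**6. Cavg labels**

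The SAP defines Cavg ("Average plasma concentration during a dosing interval") as AUC0-tau/tau for FD 1 and FD 9, but AUC0-tau is "extrapolated to the end of the dosing interval (24 h). (FD 9 only"). FD 1 Cavg cannot be derived as written. Protocol 8.3.2 asks for Cavg only on FD 9 or 10.

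**The case against.** **Later samples often rescue the area.** An 8 h or 12 h sample removes the problem, and protocol 5.1 foresees overnight stays in some cohorts to obtain them. This stands. A reader might infer that every early 6 h sample without lambda-z loses the area; the SAP's interpolation rule contradicts that. The share of subjects without a later sample is unknown.

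**A poor lambda-z is not a missing one.** This stands too. The quality criteria only flag, so the trigger is limited to too few points or no negative slope.

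**The high percentages are assumption-driven.** A reader might take about 40% of subjects, or nearly 80% of cohorts, as the size of the problem. The documents do not support that: those figures need a tmax near 3 h, half of the samples early and no later FD 1 sample.

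**The SAP does not forbid using the FD 2 predose sample.** True, but silence does not help the programmer. The convention sends that sample to time 0 of FD 2, and the partial-area rule directs that the value be dropped.

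**Accumulation can be judged otherwise.** Cmax ratios, trough summaries and 2.25 h concentrations need no lambda-z, and all PK analyses are descriptive. This limits the consequence but does not justify discarding a listed secondary endpoint that available data can supply.

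**Conclusion.** The point holds in a limited form. A compliant early 6 h draw, no later quantifiable FD 1 sample and a non-estimable lambda-z together set FD 1 AUC0-6h and the AUC accumulation ratio to missing. At a half-life above 48 h the third condition is realistic. Without an 8 h sample, simulated missingness is about 3% to about 40%. That range rests on assumed tmax, distribution phase, residual error and draw times, and the documents cannot narrow it to one figure.

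Two further inferences should be resisted. Adding the FD 2 predose sample does not by itself secure the ratio, because it repairs only the denominator. Nor is the assessment of accumulation lost, since the Cmax ratio and Ctrough remain. The FD 1 Cavg mismatch is a labelling matter. The change is worth making because it costs almost nothing, but it concerns descriptive secondary PK parameters and leaves the DLT endpoint and the MTD untouched.

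**What to change.** In SAP 16.1.2:

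1. State that, for FD 1 partial areas, the FD 2 predose concentration at its actual elapsed time since the FD 1 dose is the closing point of the profile. It keeps time 0 for FD 2 purposes.
2. For the end-of-treatment AUC0-6h, state that if the 6 h sample is early but within its window, and no later sample brackets 6 h before the next dose, the remaining 30 minutes or less are closed with the last observed concentration and flagged. Name the fraction day of the numerator for subjects on the current schedule, whose end profile is on FD 10.
3. Reconcile the Cavg and AUC0-tau labels. Removing FD 1 from Cavg is enough, as the protocol does not ask for it.

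The cost is a few sentences and a small change to the WinNonlin input, with no new samples. Item 2 is a declared exception to the SAP's rule against further imputation, so it must be written down. Its error is small. The piece is at most about 10% of AUC0-6h (twice the 15-minute share of up to 5%). A 48 h half-life gives a fall of 1 − 2^(−0.5/48) = 0.7% over 30 minutes, so the error is about half of 0.7% times 10%, or 0.04%. At an 8 h half-life the fall is 1 − 2^(−0.5/8) = 4.2% and the error about 0.2%.
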